Thereafter, a prospective cohort study evaluated outcomes in 319 adult smokers (intention to treat or ITT cohort) who underwent the full Pivot program; 272 (85.3%) participants completed the end-of-Pivot questionnaire (mean 4.1 months after enrollment) and 288 participants completed the final follow-up questionnaire three months later (mean 7.2 months after enrollment).[13,14] The Pivot program included the Pivot CO breath sensor, smartphone app, and text-based human coaching. The study included individuals along the spectrum of readiness to quit; at study entry most (66.5%, 212/319) were not thinking of quitting smoking in the next 30 days. The study examined participant engagement, changes in attitudes toward quitting smoking, and changes in smoking behavior during, at the end, and three months after active participation in the Pivot program. On average, participants had a mean of 12.4 (SD 7.1) weeks of active program engagement (defined as doing at least 1 of the following per week: completing a breath sample; logging a cigarette; starting or completing a daily activity, challenge or check-in; or messaging one's coach). Repeated measures linear mixed model analyses demonstrated positive changes in attitudes at the end of the pre-quit portion of the program, with increased confidence to quit (4.2 to 7.4, $P<.001$) and decreased expected difficulty maintaining quit (3.1 to 6.8, $P<.001$). The quit attempt rate (i.e., those making ≥ 1 quit attempt lasting ≥ 1 day) was 80.6% (232/288, completer) at final follow-up. At the end of Pivot, 7-day point prevalence abstinence (PPA) rates were 32.0% (102/319, ITT) and 37.5% (102/272, completer) which increased to 34.5% (113/319, ITT) and 39.2%

(113/288, completer), respectively, at final follow-up; 30-day PPA rates were 27.6% (88/319, ITT) and 32.4% (88/272, completer) at the end of Pivot, which increased to 31.3% (100/319, ITT) and 34.7% (100/288, completer), respectively, at final follow-up. Moreover, 30-day PPA rates were comparable among those ready and not ready to quit in the next 30 days at baseline. Of those not achieving abstinence, 25.9% (44/170, completer) achieved $\geq 50\%$ reduction in cigarettes per day (CPD) at the end of the Pivot program.

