7.3 STUDY OUTCOMES

- User engagement and retention in the program (number of app opens, number of days with at least one app open, number of weeks with at least one app open)
- Attitudes towards quitting: desire to quit, confidence to quit, difficulty to quit and self-efficacy
- Smoking behavior: quit attempts, change in cigarettes per day (CPD), smoking cessation via 7-and 30-day PPA (self-report and biochemically confirmed), continuous abstinence (self-report and biochemically confirmed), abstinence from all tobacco products, use of NRT
- Participant feedback on the set-up, use experience, design and impact of their assigned smoking cessation program

Outcomes include:

Primary:

- Total app opens in Pivot vs QuitGuide at 12 weeks (3 months)

Secondary:

- Change in expected difficulty in staying quit (participant self-report, scale 1-10) at 2, 4, 8, 12 weeks after enrollment
- Change in confidence levels towards quitting smoking (expected success in quitting, participant self-report, scale 1-10) at 2, 4, 8, 12 weeks after enrollment
- Desire to quit (yes/no) at 4 weeks after enrollment
- Self-reported abstinence (7-day and 30-day PPA) at 6, 8, 12, 26, 52 and 104 weeks after enrollment
- Self-reported abstinence (7-day PPA) at 2 and 4 weeks after enrollment
- Self-reported abstinence from all tobacco products at 6, 8, 12, 26, 52, and 104 weeks after

enrollment

- Biochemically confirmed abstinence at 12, 26, 52, and 104 weeks
 - To be considered biochemically abstinent:
 - Breath CO sample should be less than 10 ppm [16]
- Self-reported continuous abstinence at 26, 52 and 104 weeks, defined as a self-report of smoking no more than five cigarettes from 12 weeks after enrollment
 - 12 weeks is chosen because it allows for a full course of NRT, and it has been standard in studies that include pharmacotherapy for smoking cessation [17]
- Biochemically confirmed continuous abstinence at 26, 52, and 104 weeks, defined as a self-report of smoking no more than five cigarettes from 12 weeks after enrollment, and confirmation on all previous and present biovalidation tests:
 - Breath CO sample should be less than 10 ppm for participant to be considered abstinent [16]
- The proportion of participants who reduced their cigarettes per day (CPD) by $\geq 50\%$ compared to baseline at 4, 12, 26, 52 and 104 weeks

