7.4 PARTICIPANT RECRUITMENT AND INFORMED CONSENT

Participants will be recruited in the United States through web media (e.g. Facebook, Google Ads) [REDACTED]. Potential participants will be asked to provide contact information (first name, phone number, email address), and answer questions on demographics (gender, age, employment status, location via city and state, race/ethnicity), smartphone ownership, and smoking attitudes and behavior (Stage of Change and CPD) using the Online Screening Form [REDACTED]. Study staff will review each potential participant's responses to the eligibility questions.

Online screening form responses will be reviewed by study staff. Using non-proportional quota sampling, potential participants will be called on a first-come-first-served basis, as possible, with the aim to enroll 40-60% males, 40-60% females, no more than 50% of participants from any decade-spanning age group (ex. 30-39 years of age, etc.), no more than 70% of participants in the non-Hispanic white race category and up to 20% unemployed. The goals of these non-proportional quota sampling ranges are to ensure

representation among males, racial/ethnic minorities, age groups, and individuals with varying socioeconomic status. Regarding the non-proportional quota sampling for employment, at the time of protocol design (March and April, 2021) the unemployment rate in the U.S. was 6.0%.[24] Acknowledging a higher unemployment rate among people who smoke [25-28], and the desire to include individuals who either do not receive payment for their work or are not pursuing employment (stay-at-home parents, caretakers, students, retired individuals) we will enroll up to 20% of participants who do not currently have employment for which they are compensated.

During the screening phone call, potential participants will be asked questions to confirm study eligibility [REDACTED]. During this call, study personnel will inform the potential participant of the study details and will answer any questions.

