7.5 PARTICIPANT RANDOMIZATION, STRATIFICATION AND ENROLLMENT

After signing the ICF, the participant will complete an online Baseline Questionnaire. Based on responses to the questionnaire, participants will be randomly assigned in a computer-generated 1:1 manner to either Pivot or QuitGuide using randomly permuted blocks of size 2 and 4, stratified by daily smoking frequency (≤ 14 vs ≥ 15 cigarettes per day), employment status (full-time or part-time employment vs unemployed), race/ethnicity (minority race/ethnicity vs non-Hispanic White), and expected difficulty staying quit (scale 1-10; self-reported score of ≤ 5 vs. ≥ 6). After randomization, participants will be emailed the link to access their assigned group. In both groups, participants will be able to access their assigned study app from the moment of randomization and beyond (ie, after the end of the 2-year study period).

Participants will be considered enrolled after completing the following 3 tasks: electronically signing the informed consent form, completing the Baseline Questionnaire and reporting the date they first logged in to their assigned app. If participants do not complete all three criteria, they may be removed from the study.

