7.7 SAMPLE SIZE AND JUSTIFICATION

As this is a pilot RCT and first assessment of Pivot compared to usual care, the study's sample size is powered to show differences in engagement, operationalized as the number of times participants open their assigned app. Previous clinical studies assessing Pivot have reported a mean of 24.2-38.7 app opens (SD range 20.8-25.9) by 90 days (data on file). In addition, Bricker et al. reported app opens comparing ACT-based smoking cessation apps (SmartQuit and iCanQuit) to QuitGuide. In one study, at 2-month follow-up, Bricker et al. reported mean (SD) app opens were 37.2 (46.1) for SmartQuit and 15.2 (13.6) for QuitGuide.[10] In a subsequent study, at 12-month follow-up, mean (SD) app opens were 37.5 (88.4) for iCanQuit and 9.9 (50.0) for QuitGuide.[11] Based on this data, we estimate mean (SD) 25 (25) app opens in the intervention arm vs. 15 (19) app opens in the control arm at 12 weeks. To detect a difference of 10 app opens or greater between Pivot and QuitGuide with 0.8 power and 0.05 alpha would require 156.7 participants, which we round up to 158. In a previous study, 272/319 (85.3%) participants completed the end-of-Pivot questionnaire at a mean (SD) 4.1 (1.4) months after enrollment. [13,14] Considering that we will assess our primary endpoint at 3 months (12 weeks), we are accordingly including an expected 15% attrition rate, with a plan to enroll up to 180 participants (up to 90 in each arm).

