11.2 ANALYSIS

In this pilot randomized control study, changes in measurements from baseline to intra-study to exit will be assessed. Participants will serve as their own controls and comparisons will be made to no change. One sample t-test will be used for numerical data. Fisher's Exact or Chi square tests will be used for categorical data. Analyses will be conducted to calculate mean (SD) for normally distributed variables for actual data or mean (SE) for modeled data and median (interquartile range) values in instances of non-normally distributed variables. McNemar test will be used for 2-category match-paired data. Cohen kappa statistic will be used for 3-category match-paired data. Statistical significance is set at $P < .05$. All deviations from the study protocol will be identified, recorded and analyzed.

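### Randomisation is stratified on four baseline factors, but section 11.2 names no between-arm analysis that uses them; adjusting for them is a cheap improvement

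*Combined protocol and SAP*

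**What the plan says.** Section 7.5 randomises 1:1 "using randomly permuted blocks of size 2 and 4, stratified by daily smoking frequency", employment, race/ethnicity and expected difficulty staying quit. Each factor has two levels, so there are 2 × 2 × 2 × 2 = 16 strata. The Baseline Questionnaire that supplies them is completed before randomisation.

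Section 7.3 makes total app opens, Pivot against QuitGuide at 12 weeks, the primary outcome. Section 7.7 sizes the trial on that contrast: "To detect a difference of 10 app opens or greater between Pivot and QuitGuide with 0.8 power and 0.05 alpha".

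Section 11.2 treats participants as their own controls and compares with no change. For numerical outcomes: "One sample t-test will be used for numerical data". For categorical outcomes it names Fisher's exact or chi-square tests, without strata or covariates. It expects some modelling, since it reports mean (SD) "for normally distributed variables for actual data or mean (SE) for modeled data", but it names no model, covariate or type of standard error. None of the four factors reappears as an analysis variable.

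**The concern.** Stratifying on a factor that predicts outcome makes the arms more alike than simple randomisation would, so the difference in means varies less from trial to trial. An unadjusted test still puts the full outcome variance into its standard error. The standard error is then too large, the test rejects less often than its nominal 5%, and the precision that stratification bought is not used.

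The plan has little power to spare: with the expected attrition, fewer participants are evaluable than section 7.7 requires. It also leaves open what a modelled result would contain, which is a choice better closed in advance in an open-label trial.

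What is at stake is efficiency and pre-specification. The validity of the unadjusted comparison is not in question.

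**Working it through.** **1. Reproduce section 7.7.** Inputs there: 25 (SD 25) against 15 (SD 19), power 0.80, alpha 0.05, 15% attrition, up to 180 enrolled.

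- Common SD = √((25² + 19²)/2) = √493 = 22.20; standardised difference = 10/22.20 = 0.450.
- A two-sided two-sample t-test with 1:1 allocation gives a total N of 156.72, matching the stated 156.7. The plan was therefore sized on an unadjusted between-arm comparison.
- Evaluable: 180 × 0.85 = 153, below the 158 required. Unadjusted power at 153 is 0.790.

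**2. What the documents say about R².** R² here is the share of within-arm outcome variance explained by the four factors together. No section gives one. The one statement on a baseline predictor, in the Background, is that "30-day PPA rates were comparable among those ready and not ready to quit in the next 30 days at baseline". That concerns readiness to quit, which is not one of the four factors, and abstinence, not app opens. R² is therefore assumed and shown over a range.

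**3. Approximate formula.** With balanced strata, the true standard error of the difference is the unadjusted one times √(1 − R²). At 153 evaluable, the ratio of effect to unadjusted standard error is 0.450 × √153 / 2 = 2.785, and the critical value is 1.976. At R² = 0.10, √0.90 = 0.949:

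- Effect over true standard error: 2.785/0.949 = 2.936. Effective critical value of the unadjusted test: 1.976/0.949 = 2.083.
- Unadjusted null rejection: 2 × [1 − Φ(2.083)] = 3.7%.
- Unadjusted power: Φ(2.936 − 2.083) = 0.803. Adjusted power: Φ(2.936 − 1.976) = 0.831. Gain: about 2.8 points.

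The same steps at R² = 0.05 give 0.797 and 0.811, a gain of 1.4 points.

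**4. Simulation.** 180 participants were randomised in permuted blocks of 2 and 4 within 16 strata and 153 kept at random. App opens were skewed (gamma-Poisson) counts with the section 7.7 means and SDs. The factor shares were assumed (0.5, 0.18, 0.4, 0.3). The unadjusted test is Welch's; the adjusted analysis is a linear model with arm and four main effects and an HC2 standard error. There were 20,000 trials per row (Monte Carlo error about 0.3 points for power, 0.15 for null rejection).

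| Assumed R² | Power, unadjusted | Power, adjusted | Change (points) | Null rejection, unadjusted | Null rejection, adjusted |
|---|---|---|---|---|---|
| 0 | 0.803 | 0.802 | -0.1 | 4.9% | 4.9% |
| 0.02 | 0.802 | 0.806 | +0.4 | 4.7% | 4.8% |
| 0.05 | 0.803 | 0.818 | +1.5 | 4.4% | 5.0% |
| 0.10 | 0.808 | 0.835 | +2.7 | 3.9% | 4.9% |

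Smaller repeat runs, with other factor shares (including 20% unemployed and 30% minority, the limits in section 7.4) and with normal as well as skewed outcomes, gave changes of about -0.5 to +0.1 points at R² = 0, +1.0 to +1.5 at 0.05 and +2.3 to +3.2 at 0.10. Unadjusted null rejection at 0.10 ranged from 3.6% to 4.1%. The simulated unadjusted power of 0.803 differs from the 0.790 in step 1 because the counts are skewed.

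**5. Main effects or 16 cells.** Section 7.4 aims for "no more than 70% of participants in the non-Hispanic white race category and up to 20% unemployed". Eight of the 16 cells are unemployed cells, and at the 20% limit they share 0.20 × 180 = 36 participants: 4.5 per cell as randomised, and 0.20 × 153 / 8 = 3.8 when evaluable. With a dummy for every cell and HC2, the power change at R² = 0 was about -0.8 to -1.0 points, worse than with main effects.

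**6. Type of standard error.** With main effects, HC3 instead of HC2 costs about 1.4 points at R² = 0 and cuts the gain at 0.10 to about 1.7. HC2 already holds null rejection at 4.8% to 5.0% in the table, so HC3 buys nothing here.

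**The case against.** The strongest objection is that no benefit has been shown. R² is unknown, the unadjusted test is valid, and at R² = 0 adjustment gains nothing. That stands as a limit on the size of the claim. A reader might infer that ignoring the strata invalidates the comparison or inflates false positives. It does not: the error runs in the conservative direction, and only if the factors are prognostic.

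A second objection is that covariates for a test nobody has named belong with the larger gap, the absence of any between-arm test for numerical outcomes. That is a fair ranking. But whoever writes that test must decide on covariates, and the trial has already chosen and recorded the natural ones.

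A reader might also infer a power gain for abstinence. The documents do not support one. The Background rate of 32.0% (102/319) counts non-completers as not abstinent, so pairing it with 153 completers would count attrition twice; the completer rate is 37.5% (102/272). Most of that cohort (66.5%) were not thinking of quitting within 30 days, whereas this trial requires such a plan. No control rate is given, and with 76.5 per arm and 32% in Pivot, unadjusted power runs from about 0.92 at 10% control abstinence to about 0.39 at 20%.

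Lastly, the revision history shows content added for successively later visits, so 12-week data might already exist, and covariates added then would not be pre-specified. The revisions are undated, so this cannot be settled from the documents.

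**Conclusion.** The concern holds as a matter of efficiency and pre-specification. The plan balances on four factors and then names no between-arm analysis that uses them. For app opens with 153 evaluable participants, main-effects adjustment with HC2 changes power by about 0 points (-0.5 to 0) at R² = 0, about +1.5 at 0.05 and about +3 at 0.10. It also brings null rejection at R² = 0.10 from about 4% back to about 5%. These figures rest on the means, SDs and attrition in section 7.7 and on assumed R², factor shares and outcome distribution. No gain is claimed for the secondary outcomes. It is a cheap improvement worth considering, below the missing between-arm test in priority.

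**What to change.** In section 11.2:

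- **App opens (primary).** Name the between-arm analysis as a linear model with arm and the four stratification factors as main effects (not the 16 cells) and an HC2 robust standard error. Keep the unadjusted two-sample test as supportive.
- **Confidence and expected difficulty.** Use the same model with the outcome's own continuous baseline score added. For "Change in expected difficulty in staying quit (participant self-report, scale 1-10) at 2, 4, 8, 12 weeks after enrollment", that score replaces the factor cut at ≤5 against ≥6, so the same measurement does not enter twice.
- **Abstinence and ≥50% reduction in cigarettes per day.** Use logistic regression with arm and the same four factors, reported as a standardised risk difference with its variance method stated.

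The cost is wording: the factors are already recorded before randomisation, so no new data are needed. The statistical cost is up to about half a point of power if the factors are not prognostic. The text should be fixed before outcomes are examined by arm. If that has already happened, the adjusted analysis should be labelled as added later.

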	
180 adult participants (up to 90 in each arm) who report daily smoking of 5 cigarettes or more. The study will be performed remotely on an ambulatory basis. Participants will be asked to setup and use their assigned program (Pivot for intervention or QuitGuide for control). Both study arms include the option for participants to order FDA-approved nicotine replacement therapy (NRT). The study duration is 104 weeks, with the estimated active time using the program of up to 6 months and the time thereafter as follow-up. Participants will receive online questionnaires at intervals throughout the study and may undergo up to 4 videocall biovalidation study visits in which they provide breath samples using a personal carbon monoxide (CO) breath sensor, which measures CO in exhaled breath.

Data Collection	Data will be collected through participant completion of emailed online questionnaires.
Performance Variables	
Comparison between the two smoking cessation programs on:
 
 • User engagement and retention in the program • Attitudes towards quitting: desire to quit, confidence to quit, self-efficacy and difficulty to stay quit • Smoking behavior: quit attempts, change in cigarettes per day (CPD), smoking cessation via 7-and 30-day PPA (self-report and biochemically confirmed), continuous abstinence (self-report and biochemically confirmed), abstinence from all tobacco products (self-report), use of NRT • Participant feedback on the set-up, use experience, design and impact on their assigned smoking cessation program, and use of other (non-study) smoking cessation tools
Performance Endpoint and Analysis	Change from baseline measurement

Contents

1.	List of Abbreviations	7
2.	Introduction.....	8
2.1	Background	8
2.2	Study Rationale	10
2.3	Potential Risks and Benefits.....	10
2.3.1	Known Potential Risks	10
2.3.2	Known Potential Benefits.....	11
2.3.3	Risk Benefit Assessment	11
3.	Objectives	11
4.	Definitions.....	12
5.	Control – QuitGuide Plus Nicotine Replacement Therapy.....	13
5.1	QuitGuide	13
5.2	Nicotine Replacement Therapy	13
6.	Intervention - Pivot	13
6.1	Pivot Breath Sensor	13
6.1.1	Indications for Use	14
6.2	Labeling and Packaging	14
6.3	Pivot Breath Sensor Submitting a Breath Sample (Specific Steps)	14
6.4	CO Log.....	15
6.5	Pivot App.....	16
6.6	Pivot Coaching	17
6.7	Pivot Nicotine Replacement Therapy (NRT).....	17
6.8	Pivot Moderated Online Community	17
7.	Study Design and Overview	17
7.1	Study Design	17

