9. DATA COLLECTION

Study personnel will collect information from the participant over the course of the study including:

- Age
- Gender
- Pregnancy status (self-reported) in women
- Race/ethnicity
- Employment status
- Education
- Type of smartphone participant uses (iPhone or Android)
- Number of years smoking
- Social and living environment relating to smoking
 - Live with other adults who smoke
 - Live with romantic partner who smokes
 - Number of close friends who smoke
- Alcohol use (AUDIT-C, 3 items)
- Screening for depressive symptoms (CES-D, 10 items)
- Quit attempts
 - Past 12 months
 - During the study
- Number of cigarettes currently smoked per day (CPD)
- 7-day point prevalence abstinence (PPA) (self-reported and biovalidated)
- 30-day point prevalence abstinence (PPA) (self-reported and biovalidated)
- Abstinence from all tobacco products (self-reported)
- Continuous abstinence (self-reported and biovalidated)
- Use of other tobacco products other than cigarettes including pipes, cigars, cigarillos, little filtered cigarettes, hookah, water pipe, any electronic cigarette product (e-cigs, vape, vapor), smokeless tobacco, chew, or snuff, and any other inhaled combustible material
- Use of smoking cessation medications past and present
- Use of other smoking cessation methods, past and present (for the present, methods other than those in the study program)
- Attitudes towards smoking
 - Desire to quit (y/n)
 - Confidence to quit (scale 1-10)
 - Perceived difficulty of staying quit (scale 1-10)
 - Self-efficacy
- Engagement
 - App opens (self-reported)
 - Number of days with app opens (self-reported)
 - Number of weeks with app opens (self-reported)
- Feedback on assigned program set-up and use
 - Ease/difficulty getting started
 - Use experience

- Design
- Impact on quitting
- Impact on staying quit
- How would you improve the experience of your assigned program?
- How likely are you to recommend your assigned program to a friend/colleague? (scale 1-10)
- How has using your assigned program affected the number of cigarettes you smoke per day? (increase, no change, decrease)
- Which of the following best describes your thoughts on your assigned program? ('nothing else can help me with smoking' to 'it will not help me with smoking')
- Which of the following best describes your assigned program's ability to help someone quit smoking? ('extremely helpful' to 'makes quitting smoking harder')

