- Which of the following best describes what you have learned from using your assigned program ('really unique/key insights' to 'I am more confused after using the program')
- Which of the following best describes your need for your assigned program? ('I really need this program' to 'I am not interested at all in this program')
- What has been the most helpful part of your program?
- What has been the most frustrating part of your program?
- My study program helped me quit smoking – True or False
- Skills I learned in my study program have helped me stay quit – True or False
- My study program helped me with my goals related to smoking– True or False
- NRT
 - Have you ordered nicotine replacement therapy (patches, gum and/or lozenges)? Why or Why not?
 - Over the last 7 days, how many days have you used nicotine replacement therapy (nicotine patches, gum and/or lozenges)?
 - Over the last 7 days, which types of nicotine replacement therapy have you used?
 - For about how many weeks have you used NRT since the study started?
 - Since you began the study, have you purchased or obtained nicotine replacement therapy (patches, gum and/or lozenges) outside of what was provided by the study?

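### For ordered feedback items, the only between-arm test that section 11.2 leaves available is Fisher's exact or chi-square, which ignores the order; a rank or proportional-odds analysis would fit better and costs one sentence

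*Combined protocol and SAP*

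**What the plan says.** Section 11.2 describes its comparisons as within-participant: "Participants will serve as their own controls and comparisons will be made to no change". For categorical data it gives Fisher's "Exact or Chi square tests will be used for categorical data", with two paired-data rules beside it: "McNemar test will be used for 2-category match-paired data" and "Cohen kappa statistic will be used for 3-category match-paired data". It names no test that uses the order of categories, and it does not write out a between-arm test for feedback.

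The between-arm intention comes from the synopsis. There, the Performance Variables row is headed "Comparison between the two smoking cessation programs on", and participant feedback is one of its entries.

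Section 9 lists five feedback items with ordered answers:

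- effect of the program on cigarettes per day, with three stated levels ("increase, no change, decrease");
- thoughts on the program;
- the program's ability to help someone quit;
- what was learned ("Which of the following best describes what you have learned from using your assigned program");
- need for the program.

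For the last four, only the two end anchors are given, so the number of levels is unknown. No expected distribution, effect size or power is given for any of the five.

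**The concern.** The natural question for these items is whether Pivot is rated better than QuitGuide. A chi-square or Fisher test asks something looser, namely whether the two answer distributions differ in any way. If the answer columns are put in a different order, its P value does not change. It therefore cannot say which program was rated better, and it spreads a consistent shift over k − 1 degrees of freedom (k answer levels) where an ordinal test uses one. Section 11.2 asks for no effect estimate or interval that would supply the direction.

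At stake is the reading of the feedback comparison: a real, consistent preference is more easily missed, and a significant result needs a further, unplanned step to interpret. Leaving the test unspecified also leaves room to choose it after seeing the answers.

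**Working it through.** **1. Which named method can apply.** The five items concern the program a participant was assigned, so there is no value before the program and a change from baseline cannot be formed. The arms are independent groups, so McNemar and kappa do not apply. Fisher or chi-square is what remains for categorical data. If the answers were coded as numbers, the only numerical test named is a one-sample t-test, which does not compare arms.

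**2. The plan's own figure.** No power is stated for feedback. The stated sample size (section 7.7: 25 (SD 25) vs 15 (SD 19) app opens, power 0.8, alpha 0.05) does reproduce:

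- SD = √((25² + 19²)/2) = 22.20.
- Normal approximation: 4 × (22.20 × (1.960 + 0.842)/10)² ≈ 154.8 in total.
- Two-sided t-test: 156.7 in total, as stated.

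This supports reading alpha as two-sided. With 15% attrition, 180 × 0.85 = 153, or about 76 per arm.

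**3. Same signal, different degrees of freedom.** With one degree of freedom, 80% power at 0.05 needs a noncentrality of 7.85. The same noncentrality on k − 1 degrees of freedom gives:

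| Levels | Chi-square power | Loss (points) | Noncentrality for 80% | Extra participants |
|---|---|---|---|---|
| 3 | 71% | 9 | 9.63 | 9.63/7.85 = 1.23, i.e. 23% |
| 4 | 64% | 16 | 10.90 | 10.90/7.85 = 1.39, i.e. 39% |
| 5 | 60% | 21 | 11.94 | 11.94/7.85 = 1.52, i.e. 52% |

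(Losses are from unrounded values.)

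**4. Simulation at 76 per arm.** Assumed: a common odds ratio of 2.0 towards better ratings in Pivot, two-sided 0.05, Pearson chi-square against tie-corrected Wilcoxon. Each control cumulative odds is halved. For example, control 10/40/50 has cumulative probabilities 0.10 and 0.50, odds 0.111 and 1.0, halved to 0.056 and 0.5. The Pivot cumulative probabilities are then 0.053 and 0.333, which gives 5.3/28.1/66.7.

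| Levels | Control distribution (%) | Chi-square | Wilcoxon | Loss (points) |
|---|---|---|---|---|
| 3 | 10/40/50 and 10/50/40 | 46–50% | 56–59% | about 9–10 |
| 3 | uniform | 53% | 63% | about 11 (unrounded) |
| 4 | 15/30/35/20 | 48% | 65% | 17 |
| 5 | 10/20/30/25/15 and 5/10/20/35/30 | 42–44% | 65–66% | 22–23 |
| 5 | uniform | 45% | 67% | 22 |

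With no difference between arms, both tests rejected about 5% of the time, so the gain does not come from inflated error.

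**5. Wider settings.** I varied the odds ratio from 1.5 to 3.0, the levels from 3 to 7 and the size from 76 to 90 per arm. The smallest loss was about 3 points (three levels, odds ratio 3.0, 90 per arm: 94.8% vs 97.6%). The largest was about 30 (for instance seven levels, odds ratio 2.0, 90 per arm: 45% vs 75%). Three levels alone gave about 3 to 11.

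**6. Where it reverses.** If the arms differ in spread and not in position, for example 20/50/30 against 30/30/40 at 76 per arm, chi-square has about 62% power and Wilcoxon about 5%.

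**The case against.** The strongest reply is that this is a choice between two valid tests. Both hold their error rate, and chi-square is clearly better when opinions are polarised. That stands as a real downside of the change. It does not settle the matter, because the question of which program is rated better concerns a shift. Category percentages by arm would also show direction informally; that is true, but the test itself would not support the directional statement.

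A second reply is that the items might be scored as numbers. Section 2 reports mean satisfaction scores for an earlier Pivot study, and the 1–10 recommendation item may well be treated that way. The plan does not say so for the five items, and section 11.2 names no between-arm test for numerical data either.

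Third, the absence of a written between-arm analysis is a broader gap than the choice of test for feedback items. This is correct, and the change proposed here does not close that gap.

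Three stronger readings are tempting and not supported:

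- A reader might infer that every categorical variable goes to an order-blind test. Paired data are sent to McNemar or kappa, and True/False items have no order to lose.
- A reader might tie the five items to the satisfaction outcome measured at eight time points in section 7.3. Of the five, only the ability-to-help item plausibly matches one of that outcome's listed components. Section 9 gives no time points for the five items.
- A reader might take a specific power loss as a property of the plan. Level counts for four items, the distributions and the effect size are not in the documents.

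**Conclusion.** The point holds in a limited form. For between-arm comparison of the five ordered feedback items, the plan leaves only a test that ignores order. That follows from section 11.2 read with the synopsis and section 9; section 11.2 does not itself state the comparison.

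The loss of direction does not depend on any assumed figure. The loss of power does: it requires a consistent shift, and its size rests on assumed level counts, distributions and odds ratio. The 76 per arm also rests on attrition projected to 12 weeks, and would be too high for later questionnaires if fewer people respond.

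The consequence is small. The pilot is powered only for app opens and makes no power claim for feedback. Nothing here alters the app-opens or abstinence results.

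**What to change.** In section 11.2, limit Fisher's exact and chi-square tests to binary and unordered items. Add that ordered feedback items will be compared between arms by the Wilcoxon rank-sum test or a proportional-odds model, choosing one in advance. Report the common odds ratio, or the probability that a Pivot participant gives the better rating, with a 95% CI, and tabulate the category counts by arm.

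State the number and order of the answer levels for the four items that now have end anchors only.

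The cost is a sentence or two and no new data. The price is low sensitivity to differences in spread; the tabulated counts let a reader see polarised answers, though the ordinal test would not detect them.
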